#### 2.3.2 KNOWN POTENTIAL BENEFITS

There is no direct benefit to study participants.

### 3 OBJECTIVES AND PURPOSE

The objectives of the study are to establish the equivalence of DCTclock-tablet to DCTclock-pen, to establish the safety of DCTclock-tablet and Linus Platform tests administered with a tablet or smartphone, and to collect the data to enable the development and validation of Linus Platform tests.

Aim 1: Validate equivalence between DCTclock-pen and DCTclock-tablet for subjects with diverse levels of cognitive impairment

Aim 2: Characterize the safety profile of DCTclock-tablet and the Linus Platform tests

Aim 3: Obtain data to develop and validate Linus Platform tests

### 4 STUDY DESIGN AND ENDPOINTS

#### 4.1 DESCRIPTION OF THE STUDY DESIGN

This study is a randomized crossover trial consisting of two test visits separated by a washout period of 3 to 5 weeks. Subjects are randomized into two equal groups. Group 1 receives DCTclock-pen at the first visit, with the DCTclock-tablet given at the second visit; Group 2 receives DCTclock-tablet at the first visit, followed by DCTclock-pen at the second visit. At Visit 1 (day 0), eligibility is assessed and a version of the DCTclock test is administered based on the group allocation. A battery of Linus Platform tests and reference standard tests are also administered. At visit 2 (day 21-35), eligibility is assessed and the alternate version of the DCTclock test is administered based on the group allocation. A battery of Linus Platform tests is also administered, together with reference standard tests. Equivalence of DCTclock-pen and DCTclock-tablet will be tested. Linus Platform test data will be collected to develop novel measures of cognitive and motor function and assess their accuracy in detecting impairment, construct validity, and test-retest reliability. 200 subjects will be recruited to participate with the anticipation that 175 will be available for analysis.

##### 4.1.1 PRIMARY ENDPOINT

Primary endpoint:

- Equivalence of DCTclock-pen and DCTclock-tablet in assessing cognitive impairment.

##### 4.1.3 SAFETY ENDPOINT

Safety endpoint:

- Incidence of serious device related adverse events.

### 5 STUDY ENROLLMENT AND WITHDRAWAL

#### 5.1 PARTICIPANT INCLUSION CRITERIA

- Men and women 55-95 years old.

#### 5.2 PARTICIPANT EXCLUSION CRITERIA

- Ineligible for written informed consent as judged by an inability to answer three questions about study details unless a LAR is available for consent.
  - How long do the sessions last (correct response is 1.5 to 2 hours- either individual answer is also acceptable)
  - How many sessions are there (correct response is 2)
  - How much will you be getting paid (correct response will vary by site)
- Impairment of the writing hand that precludes ability to perform the study tasks. The participant will be asked whether they have suffered any significant injury or other physical change in function that would prevent them from holding a pen and writing. An answer of 'yes' would be an exclusion criteria.
- Impaired manual dexterity in the writing hand as judged by timed performance below cut-off standards (quantified by Purdue Peg Board score < 6).
- Impaired vision in both eyes as judged by poor contrast sensitivity (quantified by Hamilton-Veale Contrast Sensitivity < 7).
- Under the influence of recreational drugs or alcohol at the time of the visit.
- Current or recent (within the last 6 months) participation in a clinical trial that includes the use of a drug or intervention to alter cognitive function.
- Recent (within the last 6 months) cognitive testing with a Clock Drawing Test.
- Documented history of an MMSE or MoCA score of 18 or less or a score of 18 or less on the MMSE administered during screening unless a LAR is available for consent.
- Visit 2 Only:
  - Any self-reported change (addition or discontinuation) of the following medications between visit 1 and visit 2; Timolol (eye drop), Benadryl, beta blockers, steroids or over the counter medications for sleep (PM varieties).

### 5.3 STRATEGIES FOR RECRUITMENT AND RETENTION

The target evaluable sample size for analysis is 175. 200 participants will be screened. The anticipated accrual rate is 22 participants per month. Enrollment will be completed in ~9 months.

One to three US sites will be used in this study with competitive enrollment. Participants will be recruited from the general population and referred from neurology clinics in order to recruit subjects with a range of cognitive function. The study will be advertised in these areas using local fliers and print ads in regional papers. Participants will also be approached for participation if they are participating in other research at the sites that does not include the use of a drug or intervention to alter cognitive function and if the participant has not received a Clock Drawing Test within 6 months.

Participants will be compensated for their time at a rate of \$150 for two completed study visits. Subjects will receive \$60 for the first completed study visit and \$90 for the second completed study visit. Transportation costs will also be covered up to \$75 per study visit at the site's discretion. Maximum total payment is \$300 per subject for two completed visits. Payments will be made to the subject at the end of each visit. The study stipend may be prorated if the subject chooses not to complete all tasks on a given study visit.

### 5.4 PARTICIPANT WITHDRAWAL OR TERMINATION

#### 5.4.1 REASONS FOR WITHDRAWAL OR TERMINATION

Participants are free to withdraw from participation in the study at any time upon request. An investigator may terminate participation in the study if:

- Any clinical adverse event (AE), or other medical condition or situation occurs such that continued participation in the study would not be in the best interest of the participant.

- The participant meets an exclusion criterion (either newly developed or not previously recognized) that precludes further study participation.

#### 5.4.2 HANDLING OF PARTICIPANT WITHDRAWALS OR TERMINATION

Participants who withdraw or terminate from the study will not be pursued as the study has no follow-up or long term safety and effectiveness endpoints. Participants who withdraw or do not complete the second visit will not be replaced as the overall sample size will take into account potential withdrawals.

#### 5.5 PREMATURE TERMINATION OR SUSPENSION OF STUDY

This study may be temporarily suspended or prematurely terminated if there is sufficient reasonable cause. Written notification, documenting the reason for study suspension or termination, will be provided by the suspending or terminating party to the investigators and regulatory authorities. If the study is prematurely terminated or suspended, the Principal Investigator (PI) will promptly inform the IRB and will provide the reason(s) for the termination or suspension.

Circumstances that may warrant termination or suspension include, but are not limited to:

- Determination of unexpected, significant, or unacceptable risk to participants
- Insufficient compliance to protocol requirements
- Data that are not sufficiently complete and/or evaluable

The study may resume once concerns about safety, protocol compliance, or data quality are addressed and satisfy the sponsor, IRB and/or Food and Drug Administration (FDA).

### 6 STUDY AGENT

#### 6.1 STUDY AGENT(S) AND CONTROL DESCRIPTION

##### **DCTclock**

DCTclock-pen is Class II, 510(k) exempt medical device (12).

DCTclock-tablet is an investigational device consisting of both hardware and software. Tablet hardware includes an Apple iPad and an Apple Pencil. An iPad application captures, encrypts, and transmits the encrypted data to Linus' HIPAA compliant servers. Tests are decrypted there, analyzed using a proprietary algorithm, and presented through a reporting portal.

In DCTclock-tablet, participants are asked to draw a clock picture according to audio instructions and then copy a picture of a clock using the study supplied Apple Pencil on an iPad.

##### **Linus Platform Tests**

Linus Platform tests include both FDA cleared and investigational devices consisting of both hardware and software. Hardware includes either a study supplied Apple iPad (with or without an Apple Pencil) or a study supplied smartphone.

##### **Linus Platform drawing tasks**

Linus is developing a series of drawing-based tablet tests administered with the Apple iPad and Apple Pencil. Just like with DCTclock, an analysis of drawing behavior will be conducted to identify early indications of cognitive change. An iPad application captures, encrypts, and transmits the encrypted data to Linus' HIPAA compliant servers. These drawing-based tasks include:

- Pre-test: An exercise involving copying waves that is administered before completing the other tablet tests (including DCTclock-tablet) with the only goal of making the subject comfortable with drawing using the Apple Pencil and the iPad.
- Pathfinding test: A series of mazes to be completed as quickly and accurately as possible.
- Symbol test: Keys of symbol-digit pairs are provided followed by prompts with empty boxes where the subject is asked to input the appropriate response as quickly as possible.
- Connect test: The subject is instructed to connect a set of circles as quickly as possible according to a pre-established pattern.
- Tracing test: The subject is asked to trace a line with both their dominant and non-dominant hand.

#### **Linus Platform decision making and reaction time tests (4)**

Participants will be asked to complete three short cognitive tasks presented on a tablet supplied by the study. These tasks are sourced from DANA Brain Vital (Anthrotronix, Inc.), which is an FDA-cleared, modular application that measures cognitive efficiency by tracking subtle changes in cognitive capabilities. DANA assessments are highly sensitive and designed for high-frequency use and focus on accuracy and reaction time—two key elements of cognitive efficiency. Each task takes 1-2 minutes to complete. Subjects will also be asked to complete the PHQ-9 depression screening tool (13). An iPad application captures, encrypts, and transmits the encrypted data to Linus' HIPAA compliant servers.

The tasks included are as follows:

Task	Description
Simple Reaction Time	A bullseye stimulus appears on the screen, and the test taker taps it as quickly as possible
Procedural Reaction Time	A number (1, 2, 3 or 4) appears on the screen, and the test taker must indicate which number was displayed by tapping either the “1 or 2” button or the “3 or 4” button
Go/No-go	A building with six windows is displayed, and either a “friend” (green) or “foe” (gray) alien will appear in a window. The test taker must tap the “BLAST” button only when foe stimuli appear
PHQ-9	Self-reported depression screening tool

#### **Linus Platform speech elicitation tasks (8)**

Linus utilizes a clinical-grade speech elicitation and analytics system designed to extract outcome measures as indicators of neurological system function from research participants. Tests will be administered, and voice recordings captured and encrypted on a study provided tablet. Voice recordings are then uploaded to a secure, HIPAA compliant cloud server managed by the test manufacturer, Aural Analytics, Inc. Transcripts of the voice recordings are created, and an AI engine analyzes for finite but clinically relevant information. Algorithms apply signal processing and cognitive linguistic analysis to assess speech and fine motor skills and detect subtle changes in cognitive function. Extraction of linguistic and phonetic measures have been previously shown to correlate to Alzheimer's disease and cognitive function. Speech and voice assessments may include:

Task	Description
Complex Picture Description	Participants describe a picture of a complex scene in their own words

Category Naming	Participants name as many items as they can that belong to a category
Object Recall	Participants name a set of objects after a short delay
Sentence Reading	Participants read a set of experimentally-controlled sentences
Sustained Phonation	Participants hold out a sustained vowel sound (/a/) for as long as possible
Diadochokinetic Rate	Participants repeat a set of alternating sounds (/bVtVkV/) as quickly as possible
Story Recall	Participants recall a short story both immediately and after a delay
List Learning	3-5 words are announced, and the subject is asked to recall those words both immediately after a short delay

### **Linus Platform eye tracking-based memory assessments (9)**

VisMET (Visuospatial Memory Eye-Tracking Task) is a tablet-based application, developed by Emory University, that passively assesses visuospatial memory by tracking eye movements rather than memory judgements. VisMET offers a sensitive, and efficient memory paradigm capable of detecting objective memory impairment and predicting cognitive and disease status.

This task is conducted on an iPad and monitors a participant's gaze location and gaze patterns as they view repeated images that have been subtly changed between the first and second viewing of the image (for example, an item in the first image may have been deleted in the repeated image). This testing captures full face video recordings which will be kept and de-identified locally at the trial site. De-identified, coordinate level data will then be uploaded and a computerized algorithm will generate gaze position to approximate eye position. No other feedback from the participant is recorded. Cumulative gaze times, dwell times and other eye movement parameters serve as the study measures.

### **Linus Platform gait and balance assessment**

Cognitive decline and neurodegenerative diseases have been implicated in gait dysfunction via disturbance of top-down mechanisms and frontal-systems' resource allocation and linked to executive dysfunction (14). Gait velocity decreases, variability increases, and the ability to multitask while walking (dual-tasking) is impaired as cognition declines and can be risk indicators of dementia progression (15). These features can be captured using motion sensors, such as accelerometers and gyroscopes on smart devices, and such approaches have been validated against in-lab measures (5). Dual tasking (e.g., walking or standing while performing a cognitive task) disrupts performance in one or both tasks, and resulting dual-task costs have been shown to increase with aging and be reliable indicators of loss of cognitive reserve and development of cognitive dysfunction and early dementia (16) (17). Specifically, dual tasking activates a network of brain regions, including prefrontal cortex, and is associated with degeneration of the entorhinal cortex (18). It offers a sensitive quantitative metric of integrity of frontal systems that correlate with executive function and serve as early biomarkers of meso-temporal memory systems.

This task is conducted using a study provided smartphone carried in a pocket or phone carrier attached to the subject's waist. In the gait assessment, the subject will be asked to walk at a comfortable pace of their choosing for 45 seconds. They will then be asked to repeat that walking exercise while performing a serial subtraction task. The total time walking is < 2 minutes. In the balance assessment, the subject is asked to

stand as still as possible for 30 seconds with their eyes open. They will then be asked to stand for 30 seconds with their eyes closed, and finally, to stand for 30 seconds with their eyes open while performing a serial subtraction task. Total standing time is < 2 minutes. Data from these tasks includes gyroscope and accelerometer readings.

### **Linus Platform lifestyle questionnaire**

Adapted from the Barcelona Brain Health Initiative (7), this questionnaire includes up to 57 yes/no questions about the participant's lifestyle that are associated with cognitive performance. These questions are presented on a tablet and the subject uses their finger to select yes or no for each question.

Participants who take part in this study will also receive standard, accepted neuropsychological tests including RBANS (6) and MMSE (1) in addition to DCTclock and the Linus Platform tests.

All tests administered in this study are non-invasive and do not introduce energy into the subject. Study test results are not reported to participants or used to guide their clinical care. Additional information about the DCTclock-tablet and Linus Platform tests can be found in the Investigator's Brochure.

---

#### **6.1.1 ACQUISITION**

DCTclock-pen, DCTclock-tablet, and Linus Platform test tablet and smartphone hardware will be supplied to the sites by Linus Health, Inc. The commercially available neuropsychological tests will be purchased through standard channels.

---

#### **6.1.2 APPEARANCE AND LABELING**

##### **Hardware**

The DCTclock-tablet system hardware consists of two main components, an Apple iPad (Figure 1a) and an Apple Pencil (Figure 1b). Linus Platform tests will use the same hardware as DCTclock-tablet and also include a smartphone (Figure 1c).

**Figure 1: Study Hardware****Software**

As part of the Linus Platform, DCTclock-tablet system software consists of a locally installed iPad application to capture, encrypt, and transmit test data. The Linus Platform is a remotely hosted software platform that contains several sub-components

- Data Ingestion: Data are received and stored
- Data Processing: Data are processed and evaluated
- Presentation: Test results are presented to administrator
- Centralized administration tools: Remote devices and user accounts are managed

See DCTclock-tablet and Linus Platform Investigator's Brochure for images of Linus Platform test screens, subject instructions etc.

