**Safety endpoints:**

- Incidence of serious device-related adverse events.

Population:	Healthy adults aged 55-95
Phase:	Pivotal
Number of Sites enrolling participants:	1-3
Description of Study Agent:	
DCTclock-tablet is an investigational device consisting of both hardware and software. Tablet hardware includes an Apple iPad and an Apple Pencil. An iPad application captures, encrypts, and transmits the encrypted data to Linus' secure servers. Tests are decrypted there, analyzed using a proprietary algorithm, and presented through a reporting portal in the same manner as the DCTclock-pen assessment.
 
Linus Platform tests also consist of both hardware and software. Hardware includes either an Apple iPad and Apple Pencil or a smartphone. Linus Platform tests include additional drawing-based tasks, decision making and reaction time assessments, mood and lifestyle questionnaires, speech and voice analysis, eye-tracking based memory tests, and gait and balance measurements.

Study Duration:	9-12 months
Participant Duration:	Up to 5 weeks

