While DCTclock-pen is an easy-to-use and accurate cognitive test, enabling its administration using a tablet (DCTclock-tablet) will ease deployment by leveraging equipment more commonly found in clinical settings and that require less maintenance, with a concomitant decrease of cost and administrator burden. Hardware for DCTclock-tablet includes an Apple iPad and an Apple Pencil. Like the digital pen, the iPad captures and encrypts data as the participant draws with the Apple Pencil. In both cases – pen and tablet - the data from the DCTclock test is securely transmitted to Linus's HIPAA compliant servers where it is decrypted, then analyzed using advanced analytics including proprietary state-of-the-art artificial intelligence and machine learning techniques. Following test analysis, a report is instantly generated and immediately available for review by the investigator via a secure website. In addition to facilitating deployment by eliminating the need for unique hardware (the digitizing ballpoint pen), transitioning DCTclock to a tablet can also enable harmonization with other tablet-based cognitive assessment platforms such as the NIH Toolbox and tests under development in the Linus Platform.

The primary endpoint of this study is to determine the equivalence of DCTclock-pen and DCTclock-tablet in assessing cognitive impairment.

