## 7 STUDY PROCEDURES AND SCHEDULE

### 7.1 STUDY PROCEDURES/EVALUATIONS

Prior to initiating the study at a site, the protocol and informed consent form (ICF) will be approved by the reviewing Institutional Review Board (IRB) for the site. SRMs will be provided to each site to access all related study materials.

Site personnel involved in the study will be trained on the following items prior to administering any aspect of the study:

- Protocol
- Consent Form
- Investigator's Brochure
- Study Reference Manual
- Administration of all assessment tools including DCTclock and the Linus Platform tests.
- Data collection forms

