#### Visit 1 (Day 1) ~120 minutes total

Visit 1 Screening (40 mins)	Time Estimate
Obtain informed consent of potential participant verified by signature on written informed consent form approved by the IRB. Consent must be obtained before any study assessments are completed.	15 mins
Demographics and review of medical history and current medications	5 mins
Assessment of impairment of the dominant hand	1 min
Assessment of recreational drug or alcohol use	1 min
MMSE	10 min
Hamilton-Veale Contrast Sensitivity	3 mins
Purdue Peg Board	5 mins

If a subject screen fails at any step, they will not complete the remaining assessments; eligible subjects complete the following study assessments.

Visit 1 Study Assessments (81 mins)	Time Estimate
Brief neurological assessment	20 min
Randomized to receive DCTclock-pen or DCTclock-tablet	1 min
DCTclock-pen or DCTclock-tablet	5 mins
Linus Platform drawing tests with list learning	15 mins
Linus Platform decision making and reaction time assessments	5 mins
Linus Platform gait and balance assessments	5 mins
RBANS	30 mins

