### 7.3.2 VISIT 2 (FINAL STUDY VISIT)

#### Visit 2 (Day 21-35) ~ 94 minutes total

Visit 2 Screening (2 mins)	Time Estimate
Assessment of impairment of the dominant hand	1 min

Assessment of recreational drug or alcohol use/change in medications	1 min
--	-------

If a subject screen fails at any step, they will not complete the remaining assessments; eligible subjects will complete the following study assessments.

Visit 2 Study Assessments (92 mins)	Time Estimate
Alternate version of DCTclock from visit 1 (if DCTclock-pen version was administered, then DCTclock-tablet version is to be administered and vice versa based on randomization group allocation)	5 mins
Linus Platform drawing tests with list learning	15 mins
Linus Platform decision making and reaction time assessments with PHQ-9	10 min
Linus Platform lifestyle questionnaire	10 min
Linus Platform speech elicitation tasks	10 min
Linus Platform eye tracking-based memory assessment	5 mins
Linus Platform gait and balance assessment	5 mins
RBANS	30 min
Linus Platform reaction time assessment	2 mins

This visit ends the participant's participation in this study.

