**10.4.2 EVALUATION OF SUCCESS OF BLINDING**

N/A

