11 OTHER PLANNED ANALYSES

11.1 AGREEMENT WITH MMSE AND RBANS ANALYSES

Linus Platform individual tests will be compared to MMSE and RBANS to measure agreement in assessment of cognitive status in the Evaluable Population. Additionally, Linus Platform individual tests will be combined to obtain a Linus overall score (Linus score) to measure cognitive status: the training dataset will be used to create a Linus score based on the individual Linus Platform tests and the Evaluable Population will be used to validate the Linus score by assessing its agreement with MMSE and RBANS. I.e., all analyses below will be carried out on the Evaluable Population.

Since most of the Linus Platform tests are administered twice (once at visit 1 and once at visit 2), the RBANS is administered twice (at visit 1 and visit 2) and the MMSE is only administered once (at visit 1) the following sets of comparisons will be made:

1. MMSE at Visit 1 vs. Individual Linus Platform Score or Developed Linus Score at Visit 1
2. RBANS at Visit 1 vs. Individual Linus Platform Score or Developed Linus Score at Visit 1
3. RBANS at Visit 2 vs. Individual Linus Platform Score or Developed Linus Score at Visit 2

For each pairing of the individual Linus Platform scores or the developed Linus score and the reference standard MMSE and RBANS (Reference score), agreement analyses will be carried out as follows:

- Linus scores will be standardized by taking the subject's Linus score, subtracting by the overall Linus score mean and dividing by the overall Linus score standard deviation. This method will also be used to standardize the MMSE scores and RBANS scores. To better visualize the relationship between the two tests, the standardized Linus score will be plotted separately against a standardized reference score (either MMSE or RBANS) in a scatter plot, superimposed with a line of identity.
- Linear and rank linear regression analyses will be conducted and p-values with 95% CI will be calculated for the y-intercept and slope of each model. Either the Pearson (linear regression) or the

Spearman (rank regression) correlation coefficients will be produced and superimposed onto the scatter plots for each regression method, along with 95% CIs and the estimated regression line. In these regressions, the dependent variables are either the individual Linus Platform score or the developed Linus scores and the independent variables are either the MMSE scores or the RBANS scores.

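### The protocol does not mask RBANS examiners to index-test results, although the DCTclock report is available at once and RBANS follows in the same visit

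*Protocol*

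**What the plan says.** **Results.** Protocol 6.1.2 (Software) gives one function of the platform as "Presentation: Test results are presented to administrator". It states no timing and does not define the administrator. Protocol 2.1, describing DCTclock in both pen and tablet form, says that "a report is instantly generated and immediately available for review by the investigator via a secure website". The Protocol Summary adds that tablet results are "presented through a reporting portal in the same manner as the DCTclock-pen assessment".

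**Order.** The visit tables in Protocol 7.3.1 and 7.3.2 list RBANS last at Visit 1. At Visit 2 only a two-minute repeat of the reaction-time test comes after it. MMSE is a Visit 1 screening test, done before any device test.

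**Staff.** Under Protocol 7.1, site personnel are trained on "Administration of all assessment tools including DCTclock and the Linus Platform tests". No separate RBANS examiner is described.

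**Masking.** Protocol 10.4.1 has masking in its title but describes only blocked randomisation. Section 10.4.2, "EVALUATION OF SUCCESS OF BLINDING", is marked N/A, as is 10.4.3. The stated limits on results (2.3.1, 6.1, 7.1.1) concern participants and their clinical care.

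**Use of RBANS.** SAP 11.1 plans three sets of comparisons. Two use RBANS, the first being "RBANS at Visit 1 vs. Individual Linus Platform Score or Developed Linus Score at Visit 1" and the second its Visit 2 counterpart. SAP 11.2 compares the test-retest reliability of the Linus tests with that of RBANS.

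**The concern.** RBANS is given and scored by a person. An examiner who has just seen how a participant did on a related test may prompt, time or resolve a borderline response in line with that result. The reference then carries some of the index result, and the analysis cannot separate the two afterwards.

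What is at stake is Aim 3, the development and validation of the Linus Platform tests. RBANS is the only reference used at Visit 2, because SAP 11.1 compares the single MMSE with Visit 1 Linus scores only. The Visit 1 DCTclock report is also available three to five weeks before the Visit 2 RBANS.

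**Working it through.** The plan has no figure to reproduce here. The check has four steps.

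**1. Is a result available before RBANS?** This uses the listed minutes in Protocol 7.3.1 and 7.3.2, taking the listed order as the order of testing.

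- Visit 1: neurological assessment 20 + randomisation 1 + DCTclock 5 = minute 26. Drawing 15 + reaction time 5 + gait 5 = 25 more, so RBANS runs from minute 51 to 81 of 81. The gap is 25 minutes.
- Visit 2: DCTclock ends at minute 5. Drawing 15 + reaction time with PHQ-9 10 + lifestyle 10 + speech 10 + eye tracking 5 + gait 5 = 55 more, so RBANS runs from minute 60 to 90 of 92. The gap is 55 minutes.

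An immediate DCTclock report therefore exists before RBANS at both visits.

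**2. Which results could be seen?**

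| Result | What the documents say | Visible before RBANS? |
|---|---|---|
| DCTclock, pen or tablet | Immediate report (Protocol 2.1) | Yes, to the investigator |
| Reaction time, decision making | Tasks from an existing FDA-cleared application (6.1) | Possible; not stated |
| Drawing tests | In development (6.1); Linus algorithms to come from training data (10.3.1) | Not stated |
| Gait and balance | Phone sensor readings (6.1, 13.4) | Not stated |
| Speech | Uploaded to a partner and transcribed (13.4) | Unlikely |
| Eye tracking | Video analysed by a partner (13.4) | Unlikely |
| Combined Linus score | Built from the training data (10.3.4.1; SAP 11.1) | No |

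**3. Does anything stop it?** Neither document restricts portal access for site users, assigns a separate RBANS examiner, or masks RBANS scoring.

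**4. How large could it be?** The documents give no basis for a size, so every input here is an assumption. Let X be the Linus result, Y the unbiased RBANS and Z the DCTclock result, all standardised. Let r be the true X-Y correlation and b the shift in recorded RBANS, in SD per SD of the result seen.

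- *Direct exposure* (the examiner sees X itself): r' = (r + b) / √(1 + b² + 2br).
  - r = 0.60: b = 0.05 gives 0.65/√1.0625 = 0.63; b = 0.10 gives 0.70/√1.13 = 0.66; b = 0.20 gives 0.80/√1.28 = 0.71.
  - r = 0.40: the same three shifts give 0.44, 0.48 and 0.55.
- *Indirect exposure* (the examiner sees only Z): r' = (r + b·ρXZ) / √(1 + b² + 2b·ρYZ). With r = 0.60, b = 0.10 and both ρ = 0.5, r' = 0.65/√1.11 = 0.62. The direct case with the same r and b gave 0.66.
- *Direction, indirect case*: with the same r, b and ρYZ, r' equals r when ρXZ = 0.60 × (√1.11 − 1)/0.10 = 0.32. Agreement is inflated only for Linus tests that correlate with DCTclock more strongly than that.

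Only DCTclock is documented as visible at once, so the direct figures illustrate the less well documented route and are not an estimate for this trial.

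**The case against.** The strongest reply is that the documents never say an RBANS examiner sees anything. The line in 6.1.2 belongs to a list of software components. The line in 2.1 is product background, covers DCTclock only and names the investigator. Training staff on every tool does not mean that one person gives them all. Protocol 6.1.5 sends administration detail to the Investigator's Brochure, the DCTclock Manual and the Study Reference Manual, none of which is available here; any of them could restrict access. All of this stands. It limits the point to masking that is not specified, and does not show that examiners were unmasked.

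A reader might infer three stronger things, and the documents support none of them:

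- *Every Linus result is shown as its test ends.* Immediate availability is stated for DCTclock alone. The combined score does not exist during the visits, and speech and eye-tracking data are analysed off site.
- *RBANS is the yardstick for DCTclock.* DCTclock-tablet is compared with DCTclock-pen (Protocol 10.3.2, SAP 9.1). DCTclock matters here only as information that could influence RBANS.
- *Knowing the Visit 1 score pulls the pen-tablet pair together.* Scoring is done in code (Protocol 2.1), and the tablet test uses audio instructions (6.1). No passage shows how an administrator could move the second score towards the first.

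The reply does not remove the gap. The protocol has a section for masking, that section is silent on examiners, and one relevant result is available before the reference test at both visits.

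**Conclusion.** The point holds as a low-severity gap in the protocol. RBANS examiners are not protected from index results, and at least the DCTclock report is available before RBANS at both visits. The affected analyses are Linus-RBANS agreement and RBANS test-retest reliability, both exploratory and without a success criterion.

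The size is unknown. For agreement the bias is probably upward: always so if the examiner sees the Linus result itself (for r ≥ 0 and b > 0), and through DCTclock only for Linus tests that correlate with it well enough. For the RBANS retest benchmark the direction is open. Drift towards a result known at both visits would raise it; drift towards a different result at each visit could lower it.

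The conclusion assumes that the listed order is followed, that someone with access to results gives or scores RBANS, and that the unseen manuals contain no restriction. The MMSE comparisons are outside the concern, and no effect on the primary endpoint is shown.

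**What to change.** Add to Protocol 6.1.2 and 10.4.1 that DCTclock and Linus scores are withheld from all site users, who see only a 'test captured' status, until the participant's Visit 2 RBANS has been scored and entered. Scores are then released to the site. For participants who do not reach the Visit 2 RBANS, release the scores once their participation ends.

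Release at that point, without waiting for database lock, lets the site complete its records: Protocol 14.1 counts test results among the source documents.

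The cost is a few sentences in the protocol and study manual and a change to portal access. The platform manages user accounts centrally (6.1.2), so this looks feasible, but the documents do not confirm that access can be limited in this way. The downside is that sites cannot see scores between visits. The loss is small, because the protocol does not give results to participants or use them for care (2.3.1, 7.1.1). If a manual already imposes this restriction, a cross-reference in 10.4.1 is enough.
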